3.1.6 Per-Protocol (PP) Population

The Per-Protocol (PP) Population will be defined on the sponsor's protocol deviation guidance. The PP Population will consist of those members of the ITT Population who have no major protocol violations deemed to have a potential impact on the primary efficacy analysis.

3.1.7 Completers (CS) Population

The Study Completers (CS) Population will consist of those members of the ITT Population who have completed the entire sequence (Period II and Period IV). This population will be used for supportive analysis of the primary efficacy variable and other efficacy endpoints.

4 GENERAL CONSIDERATIONS AND HANDLING OF MISSING DATA

4.1 Definitions

4.1.1 Study Drugs

There are two study drugs being given:

- Intepirdine 35mg (Test therapy)
- Placebo (Reference)

4.1.2 Baseline

For both safety and efficacy evaluations, baseline for Period II is the pre-dose assessment at Visit 3 and baseline for Period IV is the pre-dose assessment at Visit 5.

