4.1.5 Visits and Periods

There are 5 study periods during this study:

- The Screening Period is defined as the period of time prior to the subject receiving the first dose of single-blind placebo run-in medication.
- The Single-Blind Placebo Run-In Period (Period I) is defined as the period from the first dose of single-blind run-in medication and ends on the last dose date of single-blind run-in medication. The assessments taken on the date of the first dose of randomized double-blind investigational product will be assumed to have been completed before the first dose of double-blind investigational product and will be slotted to this period.
- The First Two-Week Double-Blind Treatment Period (Period II) starts on the date of first dose of double-blind investigational product and ends on the last dose date. If the first dose of randomized investigational product is taken on the same day as Visit 3 assessments, it will be assumed that the assessments were completed before the first dose of double-blind investigational product has been taken.
- The Single-Blind Placebo Washout Period (Period III) starts one day after the last dose of the double-blind medication has been taken in Period II and lasts until the first dose of the double-blind investigational product in Period IV. The assessments taken on the date of the first dose of randomized double-blind investigational product will be assumed to have been completed before the first dose of double-blind investigational product and will be slotted to this period.
- The Second Two-Week Double-Blind Treatment Period (Period IV) starts on the date of the first dose of double-blind investigational product and ends on the last dose date. If the first dose of randomized investigational product is taken on the same day as Visit 5 assessments, it will be assumed that the assessments were completed before the first dose of double-blind investigational product has been taken.

A safety follow-up telephone call will be conducted approximately 2 weeks after completion of Period IV.

Study visits will be determined from the scheduled times as reported on the CRF. As indicated in Table 1, Schedule of Assessments visit windows of +/- 3 days are allowed for scheduling purposes. For analysis purposes in this crossover study, no visit reassignment will be used even if a visit falls before or after the scheduling window.

Table 1: Schedule of Events

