7 SAFETY SUMMARIES AND ANALYSES

The safety analysis will be descriptive in nature, and will be presented for the Safety Population. All safety data collected and captured in the CRF will be included in data listings sorted by domain, sequence, subject, and time point, or as appropriate. Mean changes from pre-treatment to on-treatment (Periods II and IV together) will be tabulated by treatment, while the number of subjects with potentially clinically significant values at pre-treatment and at the end of each double-blind two-week treatment period (Period II and Period IV) will be presented.

Generally, safety data will be presented for the Placebo Run-In Period, for the Double-Blind Treatment Period by treatment group (Period II and Period IV plus 7 days after the end of these periods, for the Washout Period starting at day 8 of the Washout Period, and for the post-treatment Follow-up Period starting at day 8 of the Follow-up Period.

All safety data will be summarized overall and then by stratified subgroup: dementia type (AD, LBD) and baseline MMSE (14-19 and 20-26).

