7.2 Clinical Laboratory

Clinical laboratory parameters will be presented using three methods:

1. Tabulations of observed values for the double-blind two-week periods pre-and post-treatment (Period II: Visit 3 and Visit 4; Period IV: Visit 5 and Visit 6) by treatment group.
2. Tabulations of the incidence of potentially clinically significant (PCS) values by treatment group. A focus will be on new-onset PCS values (ie, subjects with pre-existing PCS values at pre-treatment will not be considered to have new-onset values on-treatment). For purposes of this analysis, the most extreme (highest and lowest) value AT ANY TIME during Period II plus 7 days and Period IV plus 7 days for a parameter (for a given subject) will be used. Thus, a subject may contribute to both a low PCS value for a parameter as well as a high PCS value for that same parameter. PCS laboratory values are presented for serum chemistry in Table 2 and for hematology in Table 3.
3. Shifts from baseline to on-treatment, where values are categorized as low, normal, or high according to the lab normal values by treatment group. For purposes of this analysis, the most extreme on-treatment values will be used (most extreme low and most extreme high). On-Treatment values are considered values during Period II plus 7 days and during Period IV plus 7 days. Shifts from baseline will be based on laboratory normal ranges as provided by the central laboratory.

In addition, the incidence of TEAEs relating to hematology and serum chemistry laboratory parameters during Period II plus 7 days and Period IV plus 7 days will be presented by treatment group. These laboratory AEs will be identified from a review of the adverse events and select SOC and preferred terms will be included.

Table 2: Serum Chemistry Potentially Clinically Significant Criteria

Parameter	Gender	Low PCS	High PCS
Alanine aminotransferase (U/L)	Male	NA	133
	Female	NA	100
Albumin (g/L)	Male/Female	29	NA
Alkaline phosphatase (U/L)	Male	NA	323
	Female	NA	246
Aspartate aminotransferase (U/L)	Male	NA	118

	Female	NA	103
Direct bilirubin (umol/L)	Male/Female	NA	7.7
Total bilirubin (umol/L)	Male/Female	NA	30.8
Calcium (mmol/L)	Male/Female	1.99	2.91
Creatinine (umol/L)	Male	NA	174
	Female	NA	147
GGT (U/L)	Male	NA	136
	Female	NA	93
Creatinine clearance (mL/min)	Male/Female	59	NA
Random glucose (mmol/L)	Male/Female	2.9	NA
Potassium (mmol/L)	Male/Female	3.4	5.6
Sodium (mmol/L)	Male/Female	129	151

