7.4 ECGs

ECG data will be listed by sequence, subject, and time point. Change from baseline will be summarized by treatment group using data collected during the double-blind treatment periods plus 7 days.

The ECG analysis will include a careful review of QTcF values. As part of this review, a summary of the number (percent) of subjects with QTcF values in the following ranges will be provided: ≤ 450 msec, >450 to ≤ 480 msec, >480 to ≤ 500 msec, and >500 msec. This will be performed at ANY time during the double-blind treatment periods plus 7 days (where the highest QTcF value will be used for that assessment) and presented by treatment group.

The overall Investigator interpretation of ECG by treatment (shifts from baseline) will be tabulated. The incidence of PCS values will be presented, with a focus on new-onset PCS values in Table 5.

Table 5: List of Potentially Clinically Significant Ranges for ECG Parameters

QTcF Interval:
High: ≥ 500 msec only
High: Increase ≥ 60 msec only
High: ≥ 500 and Increase ≥ 60

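### A laboratory or ECG abnormality that first appears at Visit 5 cannot count as new under either treatment, because Visit 5 lies outside the Period II window and is also the Period IV baseline

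*SAP*

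**What the plan says.** **Baseline.** SAP 4.1.2 states: "For both safety and efficacy evaluations, baseline for Period II is the pre-dose assessment at Visit 3 and baseline for Period IV is" taken from Visit 5, before dosing. The protocol (10.4.2) defines a per-period baseline for efficacy only; the SAP extends it to safety.

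**Where Visit 5 belongs.** Under SAP 4.1.5, assessments on the first-dose date of Period IV "will be assumed to have been completed before the first dose of double-blind investigational product and will be slotted to this period", which is the washout (Period III).

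**Laboratory data (SAP 7.2).** There are three methods:
- Observed values are tabulated at the pre- and post-treatment visits ("Period II: Visit 3 and Visit 4; Period IV: Visit 5 and Visit 6) by treatment group").
- PCS incidence is tabulated with a focus on new onset, where "subjects with pre-existing PCS values at pre-treatment will not be considered to have new-onset values on-treatment".
- Shifts from baseline use the most extreme on-treatment values. The window is explicit: "On-Treatment values are considered values during Period II plus 7 days and during Period IV plus 7 days".

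**ECG data (SAP 7.4).** "Change from baseline will be summarized by treatment group using data collected during the double-blind treatment periods plus 7 days". The QTcF categories take the highest value: "This will be performed at ANY time during the double-blind treatment periods plus 7 days".

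**Washout data (SAP 7).** Safety data are also generally presented "for the Washout Period starting at day 8 of the Washout Period". The SAP does not say how that display is split or what it is compared with.

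**The concern.** Each rule is reasonable alone. Together they leave Visit 5 outside every count of new abnormalities: too late for Period II, and used as the reference for Period IV. A subject in sequence AB who is normal before and at the end of intepirdine, then abnormal two weeks later, supplies a placebo pre-treatment value and nothing else to the new-onset and shift analyses.

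Safety and tolerability is the trial's only secondary objective. In sequence AB, Visit 5 is the only routinely scheduled laboratory and ECG assessment more than 7 days after intepirdine and before the next treatment starts. In sequence BA no laboratory test or ECG is scheduled after Visit 6. A late-appearing finding after intepirdine would therefore mostly show up, if at all, in the one place where the tables treat it as a starting value for placebo.

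**Working it through.** The plan gives no figure of its own on this point, so the check applies its rules to the visit schedule.

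**Inputs**
- Visits 4 to 6 have a window of ±3 days, recalculated from the date of the previous visit (Protocol 8.1 and Table 2).
- The washout bottle is started in clinic at Visit 4 (Protocol 8.1), so the last Period II dose is at the latest about Visit 4.
- The on-treatment window is the period plus 7 days (SAP 7.2, 7.4).
- 30 to 40 subjects are randomized 1:1 (SAP 1.3, 1.4), so sequence AB has 30/2 = 15 to 40/2 = 20 subjects.

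**Step 1: can Visit 5 fall within 7 days of the last Period II dose?** Visit 5 = Visit 4 + 14 ± 3 days, that is 11, 14 or 17 days after Visit 4.
- Last dose on the day of Visit 4: the gap is 11, 14 or 17 days.
- Last dose on the day before: the gap is 12, 15 or 18 days.

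All exceed 7. At any permitted timing, Visit 5 is outside the Period II window.

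**Step 2: apply the new-onset rule.** Score each of Visits 3, 4, 5 and 6 as normal (N) or abnormal (A), which gives 2^4 = 16 patterns. New in Period II means N at Visit 3 and A at Visit 4. New in Period IV means N at Visit 5 and A at Visit 6. Two patterns are first abnormal at Visit 5:

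| Visits 3, 4, 5, 6 | New in Period II | New in Period IV |
|---|---|---|
| N, N, A, N | no | no |
| N, N, A, A | no | no |

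Neither is counted. The shift table behaves the same way, since its Period IV starting category is already abnormal.

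**Step 3: where the value does appear.** It is in the listings, in the Visit 5 observed-value tabulation (labelled by Period IV treatment), in the PCS counts at pre-treatment, and in the general washout presentation from day 8. In sequence AB:
- N, N, A, A enters overall PCS incidence at Visit 6 under placebo, and likewise the QTcF categories, which carry no baseline condition.
- N, N, A, N appears in the shift table as a return to normal under placebo.

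**Step 4: scale.** The documents give no rate for late-appearing abnormalities. With an assumed per-subject rate p, the chance of at least one among n AB subjects is 1 − (1 − p)^n:

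| Assumed p | n = 15 | n = 20 |
|---|---|---|
| 1% | 1 − 0.99^15 = 0.14 | 1 − 0.99^20 = 0.18 |
| 2% | 1 − 0.98^15 = 0.26 | 1 − 0.98^20 = 0.33 |
| 5% | 1 − 0.95^15 = 0.54 | 1 − 0.95^20 = 0.64 |
| 10% | 1 − 0.90^15 = 0.79 | 1 − 0.90^20 = 0.88 |

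**Step 5: would other rules catch both patterns?**
- Visit 5 tabulated against Visit 3 by preceding treatment captures 2 of 2.
- Visit 3 as baseline for both periods, with the windows unchanged, captures only N, N, A, A (1 of 2), and in sequence AB credits it to placebo.

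**The case against.** A period-specific baseline after a placebo washout is a coherent crossover choice. Safety here is descriptive, in a small study without a power calculation. The planned tables are specified in a separate spreadsheet (SAP 1) that is not available here, so the washout display may already be split by sequence. Washout assessments are counted from the start of Period II and flagged (SAP 4.1.4), and listings are sorted by sequence and subject, so a reader could trace an AB value at Visit 5 back to intepirdine. All of this stands. It argues for keeping the within-period baseline, but it does not supply a count of new abnormalities: the SAP text states no comparison with Visit 3 and no attribution to the preceding treatment.

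Four stronger readings are tempting, and the documents do not support them.
- *Visit 5 data are lost or left out of the laboratory tables.* They are not. The first method in SAP 7.2 tabulates Visit 5, and Step 3 above lists the other places.
- *Persistent abnormalities are missed as well.* An abnormality that starts on intepirdine and is present at Visit 4 is new-onset for intepirdine in Period II. Only late appearance falls in the gap.
- *Visit 5 is the trial's only late information.* Visit 7 may be held in clinic with further assessments (Protocol 8.1). An early termination visit includes laboratory tests and an ECG (Table 2). Clinically significant laboratory values are repeated until normal, at baseline or stable (Protocol 8.3.2.5). Clinically significant findings are also recorded as adverse events, although SAP 7.1 sends those more than 7 days after the last dose to a listing only.
- *Seven days is too short for this drug.* The documents give no half-life, so this cannot be judged from them.

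A further worsening after Visit 5, such as a QTcF rise of at least 60 msec from the Visit 5 value, would still count in Period IV.

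**Conclusion.** The point holds for laboratory and ECG abnormalities that are absent at Visits 3 and 4 and first present at Visit 5. By the SAP's own definitions the number of these reaching the new-onset PCS or shift-to-abnormal analyses is zero under either treatment, whatever their true frequency. In sequence AB, any still PCS at Visit 6 is counted in overall incidence under placebo. Because the stated rules drop or misattribute the event, this is more than missing detail.

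The size is modest and uncertain. It concerns 15 to 20 AB subjects after intepirdine, and equally BA subjects after placebo. The 14% to 88% range rests entirely on assumed rates of 1% to 10%. The conclusion also assumes that visits stay within their windows and that the ECG PCS table, for which SAP 7.4 states no separate window, follows the same period-plus-7-days rule. Efficacy is not affected.

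**What to change.** Keep the Visit 5 baseline for the within-period tables. Add to SAP 7.2 and 7.4:
- new-onset PCS and shift tables from Visit 3 to Visit 5 for laboratory and ECG data, with QTcF categories at Visit 5, by sequence (after intepirdine in AB, after placebo in BA);
- the same display for Visit 6 against Visit 3, also by sequence, with a note that a finding there is not credited to the Period IV treatment alone.

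Vital signs can be added in the same format for completeness, although SAP 7.3 sets no 7-day window. If the separate table specification already contains these displays, the SAP text need only say so. The cost is a few sentences in the SAP and one extra set of descriptive tables from data already collected. No visit, test or clinical procedure changes.

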4.1.3 Age

Age in years will be determined using the date of informed consent as recorded in the Case Report Form (CRF).

Some birth dates may be incomplete. If the month and the day are missing, we will impute January 1; if the day is missing, we will impute the 1st of the month.

4.1.4 Study Day

Study day will be calculated separately for Period II and Period IV. Day on Treatment will be calculated as the first dose date during Period II and Period IV, respectively.

- If the assessment date of interest is on or after the first dose date of Period II or Period IV, but before or on the last day of Period II or Period IV:
Day on Treatment = assessment date – first dose of Period II (or Period IV) + 1
- If Day of Assessment falls in the washout or follow-up periods, the day from the beginning of the previous period (Period II for the washout and Period IV for the follow up) will be calculated and appropriately flagged to differentiate it from Day on Treatment
- If Day of Assessment falls in the run-in or screening:
Day on Treatment = assessment date – first dose of Period II

The study day will be displayed in all relevant data listings.

4.1.5 Visits and Periods

There are 5 study periods during this study:

- The Screening Period is defined as the period of time prior to the subject receiving the first dose of single-blind placebo run-in medication.
- The Single-Blind Placebo Run-In Period (Period I) is defined as the period from the first dose of single-blind run-in medication and ends on the last dose date of single-blind run-in medication. The assessments taken on the date of the first dose of randomized double-blind investigational product will be assumed to have been completed before the first dose of double-blind investigational product and will be slotted to this period.
- The First Two-Week Double-Blind Treatment Period (Period II) starts on the date of first dose of double-blind investigational product and ends on the last dose date. If the first dose of randomized investigational product is taken on the same day as Visit 3 assessments, it will be assumed that the assessments were completed before the first dose of double-blind investigational product has been taken.
- The Single-Blind Placebo Washout Period (Period III) starts one day after the last dose of the double-blind medication has been taken in Period II and lasts until the first dose of the double-blind investigational product in Period IV. The assessments taken on the date of the first dose of randomized double-blind investigational product will be assumed to have been completed before the first dose of double-blind investigational product and will be slotted to this period.
- The Second Two-Week Double-Blind Treatment Period (Period IV) starts on the date of the first dose of double-blind investigational product and ends on the last dose date. If the first dose of randomized investigational product is taken on the same day as Visit 5 assessments, it will be assumed that the assessments were completed before the first dose of double-blind investigational product has been taken.

A safety follow-up telephone call will be conducted approximately 2 weeks after completion of Period IV.

Study visits will be determined from the scheduled times as reported on the CRF. As indicated in Table 1, Schedule of Assessments visit windows of +/- 3 days are allowed for scheduling purposes. For analysis purposes in this crossover study, no visit reassignment will be used even if a visit falls before or after the scheduling window.

Table 1: Schedule of Events

Visit Description	Screening	Beginning of Period I	Randomization / Beginning of period II	Beginning of Period III	Beginning of Period IV	End of Study	Follow-up Visit	ET ¹
Study Visit Number	V1	V2	V3	V4	V5	V6	V7	n/a
Study Week	W (-6)	W (-2)	W0	W2	W4	W6	W8	n/a
Study Day²	Up to 28 + 14 days before V2	14 +3 days before V3	0	14 ± 3	28 ± 3	42 ± 3	56 + 5	n/a
Informed consent	X							
Inclusion/Exclusion criteria	X	X	X					
Demography	X							
Medical History	X							
Concomitant medications	X	X	X	X	X	X		X
Blood alcohol and urine drug screen	X		X					
C-SSRS, Screening version	X							
C-SSRS, Since Last Visit version		X	X	X	X	X		X
Randomization			X					
Dispense IP		X	X	X	X	X		X
Assess IP compliance			X	X	X	X		X
Physical exam	X ³	X ⁴	X ⁴	X ⁴	X ⁴	X ³		X ³
Complete neurological exam ⁵	X	X	X	X	X	X		X
MRI or CT ⁶	X							
12-Lead ECG	X	X	X	X	X	X		X
Vital signs ⁷	X	X	X	X	X	X		X
Review Adverse Events	X	X	X	X	X	X	X	X
Serum OR urine pregnancy test ⁸	X		X					X
Urine pregnancy test ⁸						X		
Hep B and Hep C screen ⁹	X							
TSH, vitamin B ₁₂ , syphilis serology ¹⁰	X							
Serum chemistry	X	X	X	X	X	X		X
Hematology	X	X	X	X	X	X		X
Urinalysis	X	X	X	X	X	X		X
MMSE	X							
UPSIT	X		X	X	X	X		
Primary Gait Screen: assessment of gait speed	X	X	X	X	X	X		
Single and dual task gait assessments	X	X	X	X	X	X		
Mini BEST assessment		X	X	X	X	X		
Freezing of gait evaluation		X	X	X	X	X		
MDS-UPDRS Parts II and III		X	X	X	X	X		

Visit Description	Screening	Beginning of Period I	Randomization / Beginning of period II	Beginning of Period III	Beginning of Period IV	End of Study	Follow-up Visit	ET ¹
Study Visit Number	V1	V2	V3	V4	V5	V6	V7	n/a
Study Week	W (-6)	W (-2)	W0	W2	W4	W6	W8	n/a
Study Day ²	Up to 28 + 14 days before V2	14 +3 days before V3	0	14 ± 3	28 ± 3	42 ± 3	56 + 5	n/a
Caregiver-adapted Falls Efficacy Scale - International	X							
Handgrip strength evaluation	X							
Hachinski Ischemia Scale	X							

Abbreviations: ECG = electrocardiogram; Hep = hepatitis; IP = investigational product; mini-BESTest = mini Balance Evaluation Systems Test; MMSE = mini-mental state examination; TSH = thyroid stimulating hormone; MDS-UPDRS = Movement Disorder Society - Unified Parkinson's Disease Rating Scale; UPSIT = University of Pennsylvania Smell Identification Test

1. Early Termination visit should be performed within 7 days of stopping study drug if permanently discontinued between scheduled clinic visits.
2. If the visit window is used, the subsequent visit should be scheduled according to the date when the prior study visit actually took place and not according to the original visit schedule (ie, the subsequent visit date should be re-calculated from the date of the previous visit).
3. Full physical exam will be performed at Screening, V6, and ET; abbreviated physical exam will be performed at V2, V3, V4, and V5.
4. Brief, symptoms-directed physical examination will be performed at V2, V3, V4, and V5.
5. Neurological examinations will include assessment of gait, balance, coordination, cranial nerves, and motor and sensory systems, including assessment of peripheral neuropathy. MRI or CT will be performed between V1 and V2 if no CT or MRI scan has been performed within the previous five years since diagnosis. These scan findings must be consistent with the diagnosis of AD, DLB, or PDD without any other clinically significant pathologies.
7. Vital signs will include systolic blood pressure, diastolic blood pressure, heart rate, respiratory rate, and temperature and body weight at each visit and height at screening. Postural changes in blood pressure and heart rate will also be assessed at every visit.
8. Required only for women of childbearing potential. Either a serum or urine pregnancy test is to be performed at V1, V3, and Early Termination. A urine pregnancy test is to be performed at Visit 6. If a urine pregnancy test result is positive, an unscheduled serum pregnancy test must be performed to confirm the results.
9. If these tests were performed within 3 months prior to the planned first dose of investigational product, testing is not required. Records must be present in the subject's source documents.
10. If these tests were performed within 12 months prior to the planned first dose of investigational product, testing is not required. Records must be present in the subject's source documents.

